Mindfulness Intervention to Study the Neurobiology of Depression (MIND)

Statistical Analysis Plan

Date: 07/01/2014

Identifiers: NCT01905267 Unique Protocol ID: 2012-0689

fMRI seed-based connectivity

A 19 voxel sphere left PCC seed (-5, -50, 36, MNI coordinates) will be derived based on previous work examining PCC connectivity [23,37] and previous literature examining resting state connectivity of the PCC to probe the DMN [38-40] . Correlation coefficients will be calculated between mean time course for seed regions and all other voxels of the brain, resulting in 3-dimensional correlation coefficient images (r images), transformed to z scores using a Fisher transformation and compared in SPM8. Whole brain correction will be achieved at $p < .05$ by using AlphaSim with 1000 Monte Carlo simulations to determine a joint threshold of height and extent ($p < .005$, cluster extent of 440 mm³). A full factorial second-level model including the effects of group and time will be created. Given the current investigation was not adequately powered to detect treatment-by-time interactions; we will examine the main effect of time in the RFCBT group alone. To verify that these differences are related to treatment, we will confirm that all regions of interest (ROIs) that change from baseline to week eight in the RFCBT group do *not* change over time in the AO group. Thus, only ROIs that change in the RFCBT group and do not change in the AO group will be evaluated.

Post-hoc analyses will evaluate relations between clinical symptoms and connectivity. Two-tailed Pearson correlations between change in depression and rumination (baseline to 8 week) and change in extracted connectivity values (scan one to scan two) will be conducted.

Clinical data analyses

Mixed-effects regression models (MRMs) will be conducted on the Intent-to-Treat (ITT) sample using SPSS MIXED. MRMs allow for the dependencies inherent in repeated assessments, are robust to missing data, and can be used to estimate scores using group trajectories. MRMs will be used to assess the effects of treatment, and treatment-by-time (quadratic terms will be included and removed in the case of non-significance), on the RRS, RADS, and CDRS-R across eight weeks. Clinical results based on the sample of treatment completers as well as the fMRI sample will also be examined.

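### The whole-brain 5% rests on AlphaSim's simulated noise, not on the RFCBT t map being tested, so it is not assured in either direction

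*SAP*

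**What the plan says.** Under the SAP heading fMRI seed-based connectivity, each participant's seed correlation images are "transformed to z scores using a Fisher transformation and compared in SPM8". Whole-brain correction at p<.05 is obtained "by using AlphaSim with 1000 Monte Carlo simulations to determine a joint threshold of height and extent". The resulting threshold is voxel p<.005 with a "cluster extent of 440 mm³".

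For the model, the SAP says: "A full factorial second-level model including the effects of group and time will be created". It then narrows the test, giving limited power as the reason: "Given the current investigation was not adequately powered to detect treatment-by-time interactions", so "we will examine the main effect of time in the RFCBT group alone". Regions that pass are checked for absence of change in the AO arm. Connectivity values are extracted and their change is correlated with change in depression and rumination.

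The section names no check on the noise model and no reference distribution drawn from the data.

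**The concern.** A cluster threshold controls familywise error only if the simulated null resembles the null behaviour of the statistic being thresholded. There are two mismatches.

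- **Statistic.** AlphaSim counts clusters in simulated normal maps. A t map with few degrees of freedom forms smaller chance clusters at the same voxel p, which pushes the true error below 5%.
- **Spatial correlation.** AlphaSim assumes one Gaussian-shaped correlation. If the images also carry longer-range correlation, chance clusters are larger than simulated, which pushes the true error above 5%.

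Every later fMRI step uses the clusters that pass here. Too lenient an extent sends false regions into the AO check and the symptom correlations. Too strict an extent wastes power in a study that already reports limited power.

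**Working it through.** **Inputs from the SAP:** whole-brain target 5%; 1000 runs; height p<.005; extent 440 mm³; Fisher-z images; time effect in RFCBT alone.

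**Assumed, because the SAP does not give them:** n = 10 to 30 difference maps; 3 mm voxels; ellipsoid mask of 1.48 L; 18-neighbour connectivity; smoothness (FWHM) and correlation shape as listed below. Sidedness of the height is not stated. One-sided results are shown, and two-sided results are summarised in step 3.

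**1. The plan's own figure.** It cannot be reproduced without smoothness, mask and voxel size. In a normal-noise analogue of AlphaSim, 440/27 = 16.3 voxels. At FWHM 5 mm, an extent of 16 voxels gives 5.5% and 17 voxels gives 3.7%, so 440 mm³ corresponds to about 5% near 5 mm. The analogue needs 675 mm³ at 6 mm, 1323 mm³ at 8 mm and 2214 mm³ at 10 mm. Steps 2 and 3 use the recomputed extent, so what they show is not a complaint about the 440 mm³.

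**2. Gaussian-shaped noise, small-sample t map.** The error is the share of null data sets whose largest cluster reaches the recomputed extent (700 data sets per cell, each direction counted).

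| FWHM | n=10 | n=12 | n=16 | n=22 | n=30 |
|---|---|---|---|---|---|
| 6 mm | 0.5% | 1.0% | 1.6% | 2.4% | 2.6% |
| 8 mm | 0.8% | 1.7% | 2.2% | 2.0% | 4.1% |
| 10 mm | 1.1% | 2.1% | 2.1% | not run | not run |

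The standard error is √(p(1−p)/1400), about 0.2 to 0.5 points. Rounding the extent up to whole voxels explains little. For the normal map at 6 and 8 mm, the either-direction rates are 8.65% and 8.95%. Each direction therefore has at least half of that, 4.3% to 4.5%, against the 5% target.

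**3. Longer-tailed correlation.** The assumed form is ρ(r) = a·exp(−r²/2b²) + (1−a)·exp(−r/c), with b = 4.6 mm. The extent is the one AlphaSim would give at the FWHM obtained from first differences (7.4 to 7.8 mm). There were 600 data sets per t-map cell, with standard error about 0.6 to 1.4 points.

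| Tail | Extent | Normal map | n=10 | n=12 | n=22 |
|---|---|---|---|---|---|
| Mild (a=0.8, c=12) | 1134 mm³ | 19.6% | 5.1% | 6.4% | 12.9% |
| Medium (a=0.6, c=12) | 1107 mm³ | 36.3% | 14.7% | 18.2% | 24.9% |
| Heavy (a=0.5, c=15) | 1215 mm³ | 43.6% | 23.2% | 28.3% | 34.8% |

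The normal-map column isolates the tail effect; the n columns add the t-map effect, which pulls the other way. With a mild tail and n=10 the two cancel. Two-sided heights give the same pattern: 0.1% to 3.0% in step 2, and 3.0% to 29.8% here.

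**4. A second tail model.** With the extent again recomputed and n = 12 and 20, error was 2.0% to 2.4% with Gaussian-shaped noise, 4.8% to 6.0% with 15% of the variance long-range, and 11% to 15% with 30% long-range.

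**5. Number of runs.** With 50 exceedances in 1000, the exact 95% interval is 3.7% to 6.5% (approximately ±1.96·√(0.05×0.95/1000) = ±1.35 points). With 500 in 10,000 it is 4.6% to 5.4%. This is small beside steps 2 to 4.

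**6. The alternative.** A sign-flip largest-cluster test was run on simulated data (2 mm voxels, n=16) under three noise cases. It gave 2%, 7% and 5%, each with a standard error of about 2 points (112 data sets, 79 flips plus the observed map). That is compatible with 5%, but too small a check to show more.

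**The case against.** - **The noise model is not in the document.** The SAP names AlphaSim without describing it. The mismatch follows from how that method works, so naming the method is enough to raise it. A long tail in these images is an assumption, however, and stands as one.
- **The answer may be near 5%.** This stands. Mild tails with small n gave 5.1%, and 15% long-range variance gave 4.8% to 6.0%.
- **The sample size and degrees of freedom are unknown.** This also stands. Small n is inferred from the remark on power. The full factorial model may pool residual degrees of freedom over both arms. If larger n is taken as a rough stand-in for pooling, it moves the Gaussian case towards nominal (2.6% to 4.1% at n=30). In every long-tailed case simulated, though, error rose with n, so pooling does not rescue the 5%.
- **This is only a preference for permutation.** That would be fair if the present method delivered its stated rate across plausible inputs. It does not.

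A reader might infer that the RFCBT clusters will be inflated with false positives. The documents do not support that: they give neither n nor the spatial correlation, and the error may equally be below 5%. Nor do they support the inference that 1000 runs alone undermines the correction.

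**Conclusion.** The concern holds in a limited form. The SAP presents whole-brain p<.05 as achieved, but the AlphaSim step does not assure it for the RFCBT time map, and re-deriving the extent for the right smoothness does not cure this. Under the stated assumptions, one-sided familywise error ran from about 0.5% to 4% with Gaussian-shaped noise, through about 5% where the two effects cancel, to about 11% to 35% with heavier tails or, for a mild tail, larger n. Those limits depend on assumed sample size, voxel size, mask and tail shape. What does not depend on them is that the error varies with degrees of freedom and tail, neither of which the normal-noise simulation takes into account. The direction for this trial cannot be determined from the SAP. The change is worth making because it is cheap and replaces an assumed null with one drawn from the data.

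**What to change.** Keep the p<.005 height and replace the AlphaSim extent for the RFCBT time effect:

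1. Form each RFCBT participant's scan-two minus scan-one Fisher-z image and compute the one-sample t map.
2. Flip the signs of whole images at random, for example 10,000 times, or use all 2^n flips if that is fewer (2^13 = 8,192, so up to n=13).
3. After each flip, apply the same height threshold and record the largest cluster in either direction.
4. A cluster's whole-brain p is the share of flips, counting the observed map as one, whose largest cluster is at least as big.

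The SAP should state that this RFCBT-only paired test replaces the full factorial model for this contrast, and that it assumes differences are symmetric about zero under the null. No between-arm permutation is needed, because the plan does not say it will threshold a between-arm map. If AlphaSim is kept for description, raise the runs to 10,000.

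The cost is SAP wording and a few hours of computing, with no new data. The downsides are the loss of any degrees of freedom pooled from the AO arm and, if the required extent rises, fewer surviving clusters.

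### The second-level fMRI model tests change between two scans of the same people but names no participant factor, paired test or within-subject covariance

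*SAP*

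**What the plan says.** The section fMRI seed-based connectivity describes correlation images that are "transformed to z scores using a Fisher transformation and compared in SPM8". It then defines the second-level model: "A full factorial second-level model including the effects of group and time will be created". The treatment-by-time interaction is set aside: "Given the current investigation was not adequately powered to detect treatment-by-time interactions". In its place, "we will examine the main effect of time in the RFCBT group alone". A filter follows: "only ROIs that change in the RFCBT group and do not change in the AO group will be evaluated".

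The scans are paired within person. The post-hoc paragraph says that correlations of symptom change with "change in extracted connectivity values (scan one to scan two) will be conducted". For the second-level model itself, however, the section mentions no participant factor, difference image, paired test or correlated-error structure. By contrast, the section Clinical data analyses says explicitly that its mixed models handle the dependence between repeated assessments.

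**The concern.** When the same person is scanned twice, stable differences between people cancel out of the change. A model with group and time alone does not remove them. They stay in the error term, and the change is judged against too large a standard error.

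Two steps of the plan rest on that standard error, and the inflation affects them differently.

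- **Change in RFCBT.** Real change is harder to detect. This matters in a plan that gives low power as its reason for not testing the interaction.
- **No change in AO.** Here the plan needs a null result, so an inflated standard error is not cautious. Regions that do change in AO are more likely to pass, and this filter is the step the SAP uses to link the RFCBT change to treatment.

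**Working it through.** **Inputs from the SAP.** Two scans per participant; a factorial model with group and time; a voxel height threshold of p < .005; a time contrast in RFCBT; an AO filter. The SAP gives no power figure to reproduce.

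**Assumptions, because the SAP gives no value.** Scan-to-scan correlation r from 0 to .7; 15 participants per arm (20 as a variant); change of 0.8 or 0.5 cross-sectional SD; one-sided testing; the same .005 threshold for the AO filter; equal variance at both scans.

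**1. Standard error.** With cross-sectional SD σ and n participants in an arm:

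- true variance of the mean change = 2σ²(1-r)/n
- variance used if the scans are taken as independent = 2σ²/n
- ratio of standard errors = sqrt(2/n) / sqrt(2(1-r)/n) = 1/sqrt(1-r)

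| r | 0 | .2 | .3 | .5 | .7 |
|---|---|---|---|---|---|
| SE ratio | 1.00 | 1.12 | 1.20 | 1.41 | 1.83 |

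**2. One case by hand** (n = 15, r = .5, in units of σ).

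- True SE = sqrt(2 × 0.5/15) = 0.258. SE used without a participant term = sqrt(2/15) = 0.365.
- Without a participant term: 4(n-1) = 56 df, critical t = 2.667, so the change needed is 2.667 × 0.365 = 0.97.
- With a participant term: 2(n-1) = 28 df, critical t = 2.763, so the change needed is 2.763 × 0.258 = 0.71.
- If the true change is 0.8, the approximate power is P(Z > (0.97 - 0.80)/0.258) = 25% without the term and P(Z > (0.71 - 0.80)/0.258) = 63% with it. Simulation, which lets the estimated error variance vary, gives 27% and 63%.

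**3. Power to detect an RFCBT change of 0.8 SD** (n = 15 per arm, 20,000 simulated trials per cell).

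| r | No participant term (56 df) | Participant term (28 df) | Paired test in RFCBT alone (14 df) |
|---|---|---|---|
| 0 | 32% | 30% | 26% |
| .1 | 32% | 34% | 30% |
| .2 | 31% | 39% | 34% |
| .3 | 30% | 45% | 39% |
| .5 | 27% | 63% | 56% |
| .7 | 23% | 88% | 82% |

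The model with a participant term is ahead from about r = .1. The paired test in one arm, with fewer degrees of freedom, moves ahead between r = .1 and r = .2. With 20 per arm and r = .5 the three figures are 45%, 80% and 75%.

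**4. False positives in RFCBT without a participant term.** In large samples the one-sided error at nominal .005 is P(Z > 2.576/sqrt(1-r)). At r = .3 this is P(Z > 3.08), about .001. At r = .5 it is P(Z > 3.64), about .0001. The test is conservative.

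**5. The AO filter.** Chance that a region passes as unchanged = 1 - power, for a true AO change of 0.5 SD.

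| n per arm, r | No participant term | Participant term |
|---|---|---|
| 15, r = 0 | 1 - .107 = 89% | 1 - .099 = 90% |
| 15, r = .3 | 1 - .072 = 93% | 1 - .149 = 85% |
| 15, r = .5 | 1 - .048 = 95% | 1 - .225 = 77% |
| 20, r = .5 | 1 - .080 = 92% | 1 - .329 = 67% |

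**The case against.** The strongest reply is that the SAP is silent here, not wrong. It says the model includes group and time, not that it contains nothing else. A reader might infer that the scans will be analysed as independent, so that the standard error is certainly wrong. The text does not support that. Dependence can enter as correlated errors on the time factor, or through a paired test within RFCBT, and the SAP excludes neither. Its use of scan-to-scan change in the post-hoc correlations shows that its authors think of the scans as paired.

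This stands, and it makes the point conditional. It does not remove it. The sentence is the SAP's definition of the model, and an analyst who fitted exactly the named effects would have followed the plan and obtained the wrong error term.

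Three further replies stand in part.

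- **Power loss is not established.** It depends on r, which is not given. At r = 0 nothing is lost, and the model without a participant term is slightly ahead.
- **The error is conservative in RFCBT.** That is true for r > 0. It does not help the AO filter, where the same inflation works the other way.
- **Reading a non-significant AO result as no change is weak with any standard error.** This is also true, and it is a separate issue. The inflated standard error makes that weakness worse.

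**Conclusion.** The point holds in conditional form. The SAP specifies a second-level model for paired scans without saying how the pairing enters. If the model is run on the named terms alone and r is positive, the standard error of change is overstated by 1/sqrt(1-r). With 15 per arm, r = .5 and a 0.8 SD change, power in RFCBT is 27% without a participant term against 63% with one. For a 0.5 SD change in AO, about 95% of such regions pass the filter instead of 77%. Sample size, r, effect size, sidedness and the AO threshold are all assumptions, so these figures show the scale of the problem and do not estimate this trial's loss.

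Two stronger conclusions might be drawn, and neither is supported. One is that the plan would impose a single scan-to-scan correlation across the whole brain; the SAP mentions no such device. The other is that the RFCBT time effect should give way to a between-group test of change. That is the interaction the SAP declined to test, and whether it was right to do so is a different question from the error term.

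**What to change.** Replace the sentence that defines the second-level model so that the RFCBT time effect and the AO check are both tested within person. The SAP should name one of two routes.

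1. **Difference images.** For each participant with both scans, compute one scan-two minus scan-one Fisher-z image. Test the mean of these images against zero in RFCBT, and apply the same test in AO for the filter.
2. **Factorial model with a participant factor.** Keep group and time, add the participant factor, and take the time effect in each arm from that model. This keeps more error degrees of freedom (28 against 14 at 15 per arm) but assumes that change varies equally in the two arms.

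If a paired analysis was intended all along, one clause settles the matter. The data and the order of the analysis stay the same. The cost is fewer error degrees of freedom, and so slightly less power if r is near 0: at r = 0 and 15 per arm, 30% with a participant factor or 26% with difference images, against 32%. Participants with one scan would not contribute to the test of change; the SAP does not say how many there may be.

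### Connectivity change is attributed to treatment because it is significant in RFCBT and not significant in AO; no between-group test supports the attribution

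*SAP*

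**What the plan says.** All of this is in the SAP. Under the heading on fMRI seed-based connectivity:

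- The model: "A full factorial second-level model including the effects of group and time will be created".
- Why the interaction is not tested: "Given the current investigation was not adequately powered to detect treatment-by-time interactions". No power figure, sample size or effect size is given.
- What is tested: "we will examine the main effect of time in the RFCBT group alone".
- The purpose of the AO check: "To verify that these differences are related to treatment".
- The selection rule: "only ROIs that change in the RFCBT group and do not change in the AO group will be evaluated".

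The stated whole-brain threshold is p < .05 corrected, from height p < .005 with a 440 mm³ extent. The SAP does not say which threshold defines no change in AO, sets no equivalence margin, and does not mention direction. Connectivity values extracted from scan one and scan two are then correlated with symptom change.

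Under the heading on clinical data analyses, the treatment effect on the RRS, RADS and CDRS-R is assessed differently: "MRMs will be used to assess the effects of treatment, and treatment-by-time".

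**The concern.** The words about verification make this a claim of attribution, and an attribution to treatment needs a test of whether change differs between arms. The rule can fail in two ways.

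1. **Regions without a treatment effect can pass.** If both arms change equally, one can reach significance and the other miss it by chance. A non-significant AO result is read as absence of change. The low power that the SAP gives as its reason for avoiding the interaction makes that result more likely, so a smaller AO sample makes the check easier to pass.
2. **Regions with a larger treatment effect can be dropped.** The rule ignores direction. A region that falls in RFCBT and rises in AO shows a larger group difference than one where AO is flat, yet it is excluded because AO changed.

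At stake is the fMRI conclusion. Scanner drift, maturation, repeat-scan effects or regression to the mean, if common to both arms, could be reported as treatment effects. Any selection error also carries into the symptom correlations.

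**Working it through.** The SAP has no figure to reproduce here, so I computed the operating characteristics of the rule.

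**Inputs from the SAP:** height threshold .005 for the RFCBT map; two scans per participant; the selection rule above.

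**Assumptions:** independent arms of equal size n (10, 15 or 20); d is the true mean change divided by the SD of change; AO tested at .05 or at .005, since neither is specified. Results are per location and ignore cluster extent.

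**Formulas**

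- Within-arm power: two-sided one-sample t-test of change, df = n − 1, noncentrality d√n.
- P(pass) = power in RFCBT × (1 − power in AO).
- Direct comparison: two-sample t-test of change scores, df = 2n − 2, noncentrality (d_RFCBT − d_AO)√(n/2). With two time points this is the treatment-by-time test.

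**Step 1. Same true change in both arms, so no treatment effect.** For example, with n = 15 and d = 0.8 the noncentrality is 0.8 × √15 = 3.10. Power is 0.445 at .005 and 0.821 at .05. P(pass) is 0.445 × (1 − 0.821) = 0.080 with AO at .05, and 0.445 × (1 − 0.445) = 0.247 with AO at .005.

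| n per arm | Shared d | RFCBT significant (.005) | AO not significant (.05) | AO not significant (.005) | P(pass), AO at .05 | P(pass), AO at .005 | Direct test at .005 |
|---|---|---|---|---|---|---|---|
| 10 | 0.5 | 0.062 | 0.71 | 0.94 | 0.044 | 0.058 | 0.005 |
| 10 | 0.8 | 0.212 | 0.38 | 0.79 | 0.081 | 0.167 | 0.005 |
| 15 | 0.5 | 0.129 | 0.56 | 0.87 | 0.073 | 0.112 | 0.005 |
| 15 | 0.8 | 0.445 | 0.18 | 0.55 | 0.080 | 0.247 | 0.005 |
| 20 | 0.5 | 0.213 | 0.44 | 0.79 | 0.093 | 0.167 | 0.005 |

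The two AO columns are the chances that a region already significant in RFCBT also clears the AO check. The P(pass) columns are the overall chances of a false label. With equal n and one threshold for both arms, P(pass) = p(1 − p), where p is the common power. Its maximum is 0.25, at p = 0.5, whatever the sample size.

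**Step 2. Opposite changes.** Take n = 15.

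| d in RFCBT, AO | P(pass), AO at .05 | P(pass), AO at .005 | Direct test at .005 |
|---|---|---|---|
| 0.8, 0 | 0.423 | 0.443 | 0.221 |
| 0.8, −0.8 | 0.080 | 0.247 | 0.896 |

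Doubling the group difference cuts the chance of selection under the rule and raises the power of the direct test. In the second row AO is significant at .05 with probability 0.82, and the region is then discarded.

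**Step 3. No change in either arm.** P(pass) is 0.005 × 0.95 = 0.0048 or 0.005 × 0.995 = 0.0050, about nominal. The inflation in Step 1 needs a real change shared by the arms.

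**The case against.** The strongest reply has four parts.

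- **The RFCBT step is corrected.** If neither arm changes, the AO filter can only remove regions, and Step 3 bears this out. This stands. What is uncontrolled is the attribution to treatment when both arms change, and separating those cases is the purpose of a control arm.
- **The AO check gives some protection.** At n = 15 and a shared change of 0.8 SD, an AO test at .05 removes 82% of the regions significant in RFCBT. This also stands, but the protection depends on AO power, and it is weakest where the SAP says the study is weak. The conditional figures (up to 94%) look worse than the overall risk, so the joint rates are the ones to rely on.
- **The opposite-direction case is an extreme.** Nothing in the SAP suggests that AO would move the other way. This is fair: the shared-change problem matters more. The rule would nevertheless discard such a region.
- **The SAP disclosed the power limit, and the clinical models use a different sample and more assessments.** The difference between the two sections is therefore not a contradiction. I accept that. But disclosing low power justifies a narrower conclusion, and does not make a pair of within-arm tests a substitute for a comparison.

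The SAP does not say whether connectivity is a primary outcome, and the inference on the clinical scales is unaffected.

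**Conclusion.** The concern holds. As written, the rule can label a change common to both arms as related to treatment, and it can exclude regions with a larger group difference. Both results follow from the form of the rule: the p(1 − p) pass rate under equal change (equal n, same threshold), and exclusion whenever AO changes in either direction.

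The sizes rest on assumptions. With 10–15 scanned per arm and a shared change of 0.5–0.8 SD, the false-label probability per location is 4–8% with AO at .05 and 6–25% with AO at .005, against 0.5% for a direct test. They are not rates for a reported cluster. The rule should be corrected before any connectivity change is attributed to treatment.

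**What to change.** **Preferred.** Let the between-group comparison of change decide which regions are treatment-related. Enter one scan-two-minus-scan-one z-map per participant (or scan two adjusted for scan one), and test RFCBT against AO at the corrected threshold already stated. Delete the requirement of no change in AO. Keep the RFCBT-only map as descriptive. Report the group difference in change with a confidence interval. That estimate should not be confined to regions picked for their RFCBT change, because the selection would inflate it.

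**Acceptable alternative.** Keep the RFCBT-only analysis as the main one, delete the AO filter and the clause "To verify that these differences are related to treatment", and limit the conclusion to change over time within RFCBT.

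**Cost.** Both options need revised SAP wording; the first adds one contrast on existing images. It will also find fewer regions. With 15 per arm, a true change of 1.0 SD in RFCBT and none in AO, the direct test has noncentrality 1.0 × √7.5 = 2.74 and power of about 0.40 per location at .005. The current rule gives 0.698 × 0.95 = 0.66 with AO at .05. The extra yield comes from leaving out the sampling error of the comparison with AO. The alternative loses no power, but gives up the claim about treatment.
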